#### Infusional AEs:

Separate overall summaries of the infusional AEs will show the number and percentage of subjects who report during infusion or within 1, 24 or 72 hours after the end of infusion

- any infusional AEs,
- any serious infusional AEs,
- any nonserious infusional AEs,
- any related infusional AEs,
- any related infusional AEs by infusion,
- any serious related infusional AEs
- any infusional AEs by maximum severity
- any infusional AEs by infusion

The number and percentage of infusions temporally associated with 1 or more AEs that began during an infusion or up to 72 hours after the completion of the infusion will be displayed. This summary will be repeated for infusional ADRs.

The number and percentage of infusional AEs and of subjects with infusional AEs at each infusion (e.g. 1st infusion, 2nd infusion) will be presented for each infusion schedule. The mean number of AEs temporally associated with infusions per infusion will be calculated by (a)/(b) where: (a) equals the total number of AEs that occur during or within 72 hours of an infusion, and (b) equals the total number of infusions.

An exploratory upper 1-sided 95% exact confidence limit will be calculated for the proportion of the infusions with 1 or more infusional AEs (including nonproduct related). The proportion will be calculated as the total number of infusions with infusional AEs (AEs occurring during or within 1, 24, and 72 hours after the end of an infusion) divided by the total number of infusions. The upper 95% CI limit should be less than 0.4 to meet the FDA recommendation (FDA Guideline for industry 2008).

The number and percentage of subjects with AEs that occur during an infusion will be summarized by the infusion rate at which the AEs are reported. Further parameters will be time to onset (for infusional AEs), action taken, duration, outcome, severity, seriousness, and investigator causality.

In addition, the number and percentage of subjects with AEs occurring during infusion or within 1, 24 and 72 hours after infusion completion will also be summarized by SOC and preferred term. The same summary will be repeated for product related events (ADRs).

Listings will be provided for all AEs, AEs temporally associated with infusion (events beginning during the infusion or up to 72 hours after the completion of the infusion), severe AEs, product related AEs, serious adverse events, serious related adverse events, deaths, AEs resulting in discontinuation, AEs of special interest,. Details regarding severity, product relation, time to onset and stop of AE, information regarding infusion (e.g. infusion number, infusion rate and respective change) and AE outcome will be included as a minimum.

AEs of the same type and of any type shall be presented per subject to elucidate a possible intra subject correlation:

- One table shall enlist AEs by frequency in the following order 1. PT and 2. subject. The number and percentage of the following additional parameters shall be displayed: Seriousness, Severity, Investigator Causality, Infusional AE, Noninfusional AE,
- One table shall enlist AEs by frequency in the following order 1. per subject, 2. per SOC and 3. per PT The number of the following additional parameters shall be displayed: Seriousness, Severity, Investigator Causality, Infusional AE, Noninfusional AE.

The same shall be applied for Infections as defined in 8.2.2

**FDA Specified AE Table**: The AE table as specified below will also be presented.

Adverse reactions (FDA specification) are defined as treatment emergent adverse events, which meet any of the following criteria:

(a) Infusional AE: Adverse events temporally associated with the infusion are adverse events occurring during intravenous administration or within 72 hours after the end of infusion.

(b) Adverse events considered by the investigator to be related to administration of BT595.

(c) Adverse events for which the investigator's causality assessment was missing a worstcase scenario will be applied: The missing relationships will be imputed as 'related'.

The above defined Adverse reactions (FDA Specification), sorted by MedDRA SOC and PT, will be displayed in two columns:

• Number and percent of subjects experiencing the Adverse reaction (FDA Specification) using total number of subject as denominator.
• Number and percent of Adverse reaction (FDA Specification) using total number of infusion as denominator.

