- A subject diary (paper) will be dispensed. Full instructions on how to complete the paper diary (including information on how to identify and document AEs) will be given. Subject diaries will include a record of the following: occurrence of AEs (including infections), concomitant medication use (including antibiotic treatment), days lost from school/work due to infections and their treatment, any hospitalization, and the number of days in hospital.
- Health-related quality-of-life assessment will be performed. •
- BT595 will be infused intravenously. •
- Concomitant medications (including prohibited treatments) will be recorded. The type of concomitant medication, dose/schedule, duration, and the indication the concomitant medication was given for will be documented.
- Adverse events will be recorded. •

Treatment Period Visits (Visit 3 through Visit 19, Week 3 through Week 51 [3-Week Schedule] or Visit 3 through Visit 15, Week 4 through Week 52 [4-Week Schedule])

Subjects will attend the study site for a further 17 visits (3-week schedule) or 13 visits (4-week schedule). All assessments will be carried out before BT595 infusion, unless indicated. The following procedures will be performed at each study site visit:

- A physical examination will be performed. •
- Vital signs (pulse, blood pressure, respiratory rate) will be recorded within 30 minutes before each infusion, 15-30 minutes after the start of each infusion, 15-30 minutes after the end of each infusion, and 15-30 minutes after the start of any change in the infusion rate. In any case where the change in infusion rate is sooner than a 15 minute interval, vital signs should be measured prior to the change.
- The vital sign, temperature, will be recorded within 30 minutes before each • infusion only.
- Body weight will be recorded (to calculate subject dose).
- A urine pregnancy test (dipstick) will be performed for all female subjects of • child-bearing potential (≥12 years of age or presence of menstruation at screening).
- Samples for routine safety laboratory parameters (hematology, coagulation, • clinical chemistry, urinalysis) will be taken.
- Samples for IgG trough levels (total IgG) will be taken. The subject's total IgG • trough level result from the previous infusion will be made available before the infusion of BT595 to allow dose adjustment if a subject's trough level was below 5 g/L.
- A subject diary (paper) will be collected and reviewed. ٠

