Where appropriate, analyses of AEs should take into account the observed intra-subject correlation of the same type or any type of AE, as such within-subject events may not be independent. Methodology for these analyses will be described in the Statistical Analysis Plan (SAP).

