Adverse events will be coded using the most current version of MedDRA. The version used will be defined in the SAP. Incidence rates (i.e., number and percentage of affected subjects) will be calculated for the coding levels *system organ class* and

preferred term. Further analyses of AEs will focus on seriousness, intensity, causal relationship to study medication, and outcome. Immediately reportable AEs (including SAEs etc) will be displayed in detail. Where appropriate, analyses of AEs will consider the observed intra-subject correlation of the same type or any type of AE, and as such within-subject events may not be independent. Methodology for these analyses is described in the SAP.

An exploratory 2-sided 90% confidence limit interval will be calculated for the total number of subjects with TEAEs and for the number of subjects with infusional AEs (i.e., AEs within 72 hours after the end of infusion).

An exploratory upper 1-sided 95% confidence limit will be calculated for the proportion of the infusions with 1 or more temporally-associated AE (including nonproduct related). The proportion will be calculated as the total number of infusions with infusional AEs (AEs occurring during or within 1, 24, and 72 hours after the end of an infusion) divided by the total number of infusions.

All AEs will be captured and registered (listed) and will include separate reports of all AEs and of all AEs judged by the investigator to be associated with the BT595 infusion, even if the sponsor determines the AE not to be product-related.

Safety laboratory assessments will be categorized with respect to the laboratory specific reference ranges as normal/abnormal. Abnormal values will be further classified with respect to clinical relevance. Changes over time will be described by means of "shift-tables". The raw data will be listed. Values below or above the reference values in the data listings will be flagged. All laboratory values will be converted into common units for presentation reasons.

Intravascular hemolysis laboratory assessments will be summarized by the number and percentage of subjects and infusions with the given results at each visit. In case of positive Coombs' test results, further evaluations and/or time points will be included in the summaries.

For the viral safety parameters (retention samples), the presentation of the data will be detailed in the SAP.

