#### 3.3. BRIEF DESCRIPTION

Study 991 is a Phase III pivotal, open-label, prospective, uncontrolled, multicenter study investigating clinical efficacy, safety, and PK properties of the human normal immunoglobulin BT595 for intravenous (iv) administration as replacement therapy in subjects with PID.

The study is planned to be conducted in about 25 sites in Europe (Germany, Spain, United Kingdom, Hungary and Russia) and in the United States.

The study population includes male and female subjects aged 2 through 75 years with PID. For those countries where local regulations permit enrolment of adult subjects only, subject recruitment is restricted to those who are 18 through 75 years.

About 70 subjects will be enrolled to ensure data are available for at least 50 evaluable subjects. Amongst those subjects at least 20 subjects are to be adults (17 resp. 18 to <76 years,) and at least 20 subjects are to be pediatric (i.e., young children [2 to <6 years], children [6 to <12 years] or adolescents [12 to <17 resp. <18 years]). The age distribution represents the PID patient population.

According to FDA advice from January 12, 2017 for Pediatric Study Plan, age groups are defined as stated in the FDA 2016 guideline for pediatric study plans differently for the US: The age group of adolescents for the US is restricted to 12 to <17 years and therefore only subjects 2 to <17 years can be enrolled into the group of pediatric subjects.

A DSMB is to be established in this study to monitor the safety data. At least 10 adult subjects (18 to <76 years) who have received at least 2 BT595 infusions will be reviewed by the DSMB before any pediatric subjects are enrolled to the study. The DSMB reviews the safety data and provides recommendations on the suitability of the enrolment of pediatric subjects in the study depending on the assessment of possible safety concerns. However, the final decision to enroll/not enroll pediatric subjects is the responsibility of the sponsor.

BT595 is administered at 3- or 4-week intervals for a treatment period of approximately 12 months. The initial dose and dosage intervals are chosen to be consistent with the

subject's prestudy IVIg treatment and the initial dose and dosage interval are only changed if medically indicated. This change will be at the investigator's discretion.

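### The infusional-AE limit compared with 0.4 treats infusions as independent, so it is too low if AEs cluster within subject, and no clustered limit is planned

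*SAP*

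**What the plan says.** SAP 11.3, under Infusional AEs, plans the following: "An exploratory upper 1-sided 95% exact confidence limit will be calculated for the proportion of the infusions with 1 or more infusional AEs". The numerator is infusions with at least one AE during the infusion or in the 72 hours after it, related or not. This count is "divided by the total number of infusions". The SAP then sets a benchmark: "The upper 95% CI limit should be less than 0.4 to meet the FDA recommendation".

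On correlation, Protocol 9.2.3 says: "Where appropriate, analyses of AEs should take into account the observed intra-subject correlation of the same type or any type of AE". Protocol 10.7, which also introduces this limit (without the word exact and without the 0.4), repeats that "within-subject events may not be independent. Methodology for these analyses is described in the SAP".

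The SAP's answer is in 11.3: "AEs of the same type and of any type shall be presented per subject to elucidate a possible intra subject correlation". It consists of two frequency tables, one ordered by preferred term and subject, the other by subject, system organ class and preferred term. No interval or model that allows for clustering appears in SAP 6.1 or 11.3. SAP 13, which lists departures from the protocol, does not mention the point.

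**The concern.** The infusions are repeated observations on the same people. An exact limit on x of n infusions uses the binomial distribution, which takes the n infusions as independent. The SAP does not state that assumption; it follows from the method.

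The protocol gives reasons to expect positive correlation. Section 6.10 refers to subjects who are prone to infusion-related AEs. Section 6.4 reports that in the earlier 10% product's study 16 of 25 subjects tolerated 6 or 8 mL/kg/h while 4 of 25 had maximum tolerated rates under 4. Section 8.4 says the risk of hypersensitivity reactions rises with infusion rate. None of this gives the size of the correlation.

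Under positive correlation the pooled proportion varies more than the binomial allows, so the upper limit sits too low. The report could then say that the 0.4 benchmark is met when a limit with proper coverage would not support it. This is also the one AE quantity that the SAP sets against a number, so it is where the protocol's undertaking on correlation matters most.

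**Working it through.** **Inputs**

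- Infusions per completer: the baseline infusion plus 13 further treatment visits (4-week) or 17 (3-week), so 14 or 18 (Protocol 7.1).
- Subjects: "About 70 subjects will be enrolled to ensure data are available for at least 50 evaluable subjects" (SAP 3.3). Planned infusions therefore run from 50 × 14 = 700 to 70 × 18 = 1,260. I use 60 × 15 = 900 as a middle case.
- Limit: upper 1-sided 95%, exact; benchmark 0.4 (SAP 11.3).
- Within-subject correlation ρ: not in the documents. I assume 0.05 to 0.3, with 0 for reference.

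The documents state no computed value for this limit, so there is no plan figure to reproduce.

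**Step 1. How often the exact limit falls below 0.4 when the true proportion is 0.40.** The count per subject is drawn as beta-binomial with correlation ρ, and the Clopper-Pearson 1-sided limit is computed on the pooled infusions. A valid 95% limit should fall below 0.4 in at most 5% of trials.

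| ρ | 60 × 15 | 50 × 14, 50 × 18, 70 × 14, 70 × 18 |
|---|---|---|
| 0 | 4.7% | 4.5–4.8% |
| 0.05 | 9.9% | 9.7–10.9% |
| 0.1 | 14.1% | 13.6–15.6% |
| 0.2 | 19.6% | 19.1–21.5% |
| 0.3 | 23.2% | 22.9–25.0% |

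In the same trials a limit built from subject-level variation (ratio estimator, t quantile on subjects minus 1 degrees of freedom) falls below 0.4 in 5.0–5.6% of trials in every setting.

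**Step 2. Size at one observed value.** Approximate clustered limit: p + 1.645 × √[p(1 − p) × DEFF / N], with DEFF = 1 + (m − 1)ρ. For m = 15, DEFF is 1.7, 2.4, 3.8 and 5.2 for ρ = 0.05, 0.1, 0.2 and 0.3.

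- Observed 324/900 = 0.36. The exact limit is 0.387. The independent standard error is √(0.36 × 0.64 / 900) = 0.016, and 1.645 × 0.016 = 0.0263. Multiplying by √DEFF and adding 0.36 gives 0.394, 0.401, 0.411 and 0.420. The comparison with 0.4 changes from ρ = 0.1 upwards.
- Observed 270/900 = 0.30. The exact limit is 0.326, and the clustered limit at ρ = 0.3 is 0.357. Both are below 0.4.

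**Step 3. Where the comparison changes.** With N = 900 the exact limit is 0.3996 at 335 infusions with an AE (0.372), the largest count that passes. The clustered limit reaches 0.4 or more from 330, 324, 315 or 307 infusions for ρ = 0.05, 0.1, 0.2 or 0.3. The affected bands are:

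| Infusions | ρ = 0.05 | 0.1 | 0.2 | 0.3 | Upper end |
|---|---|---|---|---|---|
| 700 (m = 14) | 0.363 | 0.356 | 0.344 | 0.336 | 0.369 |
| 900 (m = 15) | 0.367 | 0.360 | 0.350 | 0.341 | 0.372 |
| 1,260 (m = 18) | 0.370 | 0.363 | 0.354 | 0.346 | 0.376 |

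A Clopper-Pearson limit on the effective sample size N/DEFF gives slightly lower starting points for N = 900: 0.364, 0.358, 0.347 and 0.337.

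**The case against.** The limit is called exploratory in both documents, and SAP 11 describes the safety results as descriptive. No decision rule hangs on it, so the error rates in Step 1 describe a decision the plan does not formally make, evaluated exactly on the boundary. The affected band is narrow and nothing in the documents places this trial inside it. The only related figure, 11.5% of infusions with adverse drug reactions for an earlier product (Protocol 1), would pass either way. The value of ρ is assumed. The protocol's commitment is qualified by where appropriate, and the SAP did respond with tables. Finally, the 0.4 is attributed to FDA guidance that cannot be consulted here and may have been meant for an unadjusted limit.

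Most of this stands as a bound on importance, and the narrow band and assumed ρ are conceded. It does not remove the fault. The 11.5% counts related events only, while the planned numerator takes any AE within 72 hours, so it cannot exclude the band. Tables can reveal clustering but cannot correct a limit. Outside the band, a figure labelled 95% would still lack that coverage. The uncertainty about the guidance is a reason to keep showing the exact limit, not a reason to omit the clustered one.

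**Conclusion.** The concern holds. The planned limit keeps its level only if infusions within a subject are independent, which the protocol itself says may not be so, and the SAP supplies no method that allows for correlation. For ρ between 0.05 and 0.3 the nominal 5% error at a true proportion of 0.40 becomes roughly 10% to 25% over the planned range of trial sizes. Whether the statement about 0.4 would change depends on the observed proportion falling in the bands of Step 3.

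The result rests on positive within-subject correlation, an assumed ρ, a beta-binomial model, and full completion with equal numbers of infusions per subject. The direction of the error is certain under positive correlation; its practical effect in this trial is not known. It should be corrected, but it bears on an exploratory safety statement and not on the primary efficacy analysis.

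**What to change.** In SAP 11.3, keep the point estimate (infusions with an AE over all infusions) and show the exact limit as a descriptive figure, so that a reading of the benchmark on an unadjusted limit remains available. Add a 1-sided 95% upper limit clustered by subject and base the comparison with 0.4 on it. Suitable methods are a ratio estimator or GEE with subject-level sandwich variance and a t quantile on subjects minus 1 degrees of freedom, or a bootstrap that resamples subjects. Report the estimated within-subject correlation beside it.

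This needs one or two sentences and a standard procedure, with no new data. The price is a higher limit, which less often falls below 0.4 when the true proportion is below 0.4. For 60 × 15:

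| True proportion | ρ | Exact | Clustered |
|---|---|---|---|
| 0.35 | 0.1 | 82% | 64% |
| 0.35 | 0.2 | 77% | 48% |
| 0.35 | 0.3 | 73% | 39% |
| 0.30 | 0.1 | 99.9% | 99% |
| 0.30 | 0.3 | 98% | 86% |

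That loss is what correct coverage costs when the data are clustered. With no clustering there is almost none.

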6.2 Dosage and Administration

The planned dose of BT595 is 0.2 to 0.8 g/kg body weight (bw; 2 to 8 mL/kg) administered as intravenous infusions at 3- or 4-week intervals for a treatment period of approximately 12 months.

Infusion rate: BT595 should be infused intravenously at an initial rate of 0.3 mL/kg/h for 30 minutes, to be increased to 1.4 mL/kg/h for a further 30 minutes. If well tolerated, the rate of administration may then be gradually increased to a maximum of 2.0 mL/kg/h for the remainder of the first infusion. Every infusion must start again at an initial rate of 0.3 mL/kg/h. From the second infusion, in subjects who have tolerated the infusion rate of 2.0 mL/kg/h well, the rate may be gradually increased to 4 mL/kg/h, and

if still tolerated well, it may be further increased gradually to 6 mL/kg/h, and to a maximum of 8 mL/kg/h.

From the second infusion, subjects' infusion rates may be individually tailored (i.e., a certain infusion rate for a certain time period) at the discretion of the investigator, but must start again at an initial infusion rate of 0.3 mL/kg/h. This means that the 30 minute interval may be shortened to less than 30 minutes if deemed appropriate for the subject. Changes in infusion rates (increases and/or decreases) and the respective time of day must be documented.

In case of a decrease in infusion rate or an interruption of infusion as a consequence of an AE, all AE details must be recorded in the eCRF.

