10.7 Safety Analysis

The safety endpoints will be summarized descriptively.

Adverse events temporally associated with the infusion are AEs occurring during infusion or within 1, 24, and 72 hours after the end of infusion and will be defined as infusional AEs. Summaries of AEs will be based on TEAEs, defined as those events with onset date/time at or after the first infusion date/time. All AEs will be attributed to the most recently received infusion rate at the time of onset. Presentation for TEAEs will be done overall. The safety analysis has to consider the severity, causality, and seriousness of AEs.

Safety issues will mainly be addressed by measuring:

- The number of infusional AEs (including nonproduct related; occurring during infusion or within 1, 24, and 72 hours after the end of infusion).
- The number of related infusional AEs (occurring during infusion or within 1, 24, and 72 hours after the end of infusion).
- The number of infusional AEs (occurring during infusion or within 1, 24, and 72 hours after end of infusion) by infusion (e.g., 1st infusion, 2nd infusion, etc).
- The number of serious infusional AEs (occurring during infusion or within 1, 24, and 72 hours after the end of infusion).
- The number of nonserious infusional AEs (occurring during infusion or within 1, 24, or 72 hours after the end of infusion).
- The number of infusions temporally (within 72 hours) associated with 1 or more infusional AEs.
- The number of all AEs.
- The mean number of AEs temporally associated with infusions per infusion.
- The number of TEAEs (infusional and noninfusional).
- The number of TEAEs (noninfusional).
- The number of serious TEAEs (infusional and noninfusional).
- The number of serious TEAEs (infusional).
- The number of serious TEAEs (noninfusional).
- The number of related TEAEs (non infusional).
- The number of serious related TEAEs (noninfusional).
- The number of TEAEs by maximum severity (noninfusional).
- The number of TEAEs leading to study drug infusion interruption and/or study drug infusion stop.
- The number of TEAEs leading to premature withdrawals.
- The number of TEAEs of special interest.
- The number of ADRs.
- The number of expected/unexpected TEAEs or ADRs.
- Changes in safety laboratory parameters (outside reference range and clinically relevant).
- Results of intravascular hemolysis parameters (number of positive hemolysis test results).
- Changes in vital sign parameters.
- Changes in physical examination parameters.

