# 6. GENERAL ASPECTS FOR STATISTICAL ANALYSIS

#### 6.1. GENERAL METHODS

Data from all subjects collected in this study will be documented with the help of subject data listings. Summary tables will be provided for all patients, except screen failures.

Generally, descriptive statistics will be provided by treatment schedule (3- or 4- week) and overall. Additionally by dosage and by observation time (visit), if applicable. Only scheduled visits/time points will be presented in summary tables. Data from unscheduled visits will be listed only.

Quantitative (continuous) data - absolute values and changes from baseline, where appropriate - will be summarized with number of observations (n), arithmetic mean, standard deviation (SD), median, minimum, and maximum. Confidence intervals, 25th percentile and 75th percentile will be added where applicable.

Qualitative (categorical) data will be summarized using number of observations (n), and frequency and percentages of subjects. Unless stated otherwise, the calculation of percentages will be based on the total number of subjects in the set of interest. Thus, counts of missing observations will be included in the denominator and presented as a separate category. Confidence intervals will be added, where applicable.

All data will be listed for the All Subjects Enrolled Set, sorted by subject number and time of occurrence (visit, start of event) whereas treated subjects will be sorted above screening failures.

Shells for summary tables, figures, and subject listings are described in a separate document, which is seen as an Appendix to the SAP. Templates for each unique table, figure, and listing are provided. These provide only a draft indication of the content and appearance of the tables, figures, and listings, and the final output may vary in appearance from these templates.

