## 11. SAFETY

All analyses described in this section will be performed using the SAF and will be presented by treatment schedule (3- or 4 week) and overall, if not stated otherwise. The results will be descriptive in nature. All data will be summarized and listed.

In addition, all safety parameters will be presented stratified by age categories, gender, race and region as defined in Section 6.6. Age classes will be presented separately by FDA and by EMA criteria. The pediatric population (young children, children and adolescents) will be presented as a subtotal.

Safety will be assessed on the basis of AEs, laboratory parameters (routine safety and intravascular hemolysis), vital signs, and physical examination.

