## 15.3.4.2. Table Conventions

- Units will be included where available.
- A missing category will be added to any parameter for which information is not available for 1 or more subjects.
- Percentage values will be printed to one decimal place. If a value rounds down to 0.0 then display as '<0.1'. Unless otherwise noted, for all percentages, the number of subjects in the analysis set will be the denominator. Percentages equating to 100% will be presented as 100%, without any decimal places. Zero percentages will not be presented and so any counts of 0 will be presented as 0 and not as 0 (0%).
- Unless otherwise specified, mean, median, and percentile values will be presented with one decimal more than the original value, SD will be displayed with two decimals more than the original value and minimum/maximum values will have the same number of decimals as the original value.
- P-values will be output in the format: "0.xxxx", where xxxx is the value rounded to 4 decimal places. Any p-value less than 0.0001 will be presented as <0.0001. If the p-value is returned as <0.9999 then present as <0.9999.
- Missing descriptive statistics or p-values which cannot be estimated will be reported as "-".

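### SAP 11.3: by default the table of AEs by infusion rate divides by all treated subjects, so percentages at higher rates are diluted relative to the risk among subjects who received them

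*SAP*

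**What the plan says.** The table is defined in SAP 11.3, under infusional AEs: the "number and percentage of subjects with AEs that occur during an infusion will be summarized by the infusion rate at which" they are reported. That sentence gives no denominator.

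Three other places in the SAP supply one:

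- SAP 6.1: "Unless stated otherwise, the calculation of percentages will be based on the total number of subjects in the set of interest".
- SAP 15.3.4.2, unless otherwise noted: "for all percentages, the number of subjects in the analysis set will be the denominator".
- SAP 11: "All analyses described in this section will be performed using the SAF". The Safety Set is everyone with at least one dose.

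Nothing else in 11.3 overrides this for the rate table. Where 11.3 wants a different base it says so: the proportion of infusions with an infusional AE and one column of the FDA-specified table both use total infusions. Neither is split by rate.

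On attribution, Protocol 10.7 says "All AEs will be attributed to the most recently received infusion rate at the time of onset". On data, Protocol 6.2 says "Changes in infusion rates (increases and/or decreases) and the respective time of day must be documented".

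SAP 11.1 summarizes the highest infusion rate given, in six categories with everything above 6 mL/kg/h pooled. It also summarizes changes to the planned rate and the duration of each infusion.

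**The concern.** Subjects do not all receive the same rates. Every infusion starts at 0.3 mL/kg/h, the first is capped at 2.0 mL/kg/h, and later increases depend on tolerance (Protocol 6.2). A subject who never receives 6 or 8 mL/kg/h cannot have an AE at that rate, yet stays in the denominator and counts as event-free there.

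Tolerability by rate is a question the study sets itself. Protocol 8.4 says rates from 0.3 to 8 mL/kg/h will be assessed and that hypersensitivity-type reactions increase with rate. Protocol 9.2.3 requires the rate at AE onset to be reported and analyzed. The 11.3 table is the planned answer, and a reader will compare its rate categories with one another.

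**Working it through.** **The plan's own figure.** Neither document gives an expected AE percentage by rate, so there is none to reproduce. The one related figure checks: Protocol 6.4 reports 16 of 25 subjects in Part B of the earlier 10% product's study with a maximum tolerated rate of 6 or 8 mL/kg/h at their fourth infusion, and 16/25 = 64.0%.

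**Step 1: effect of the denominator.** Let N be all treated subjects, n those who received the rate, and x those with an AE at it.

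Shown percentage = x/N = (n/N) × (x/n) = share exposed × risk among the exposed.

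This can never exceed the risk among the exposed, and is lower whenever n < N. For a 10% risk among the exposed:

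| Share reaching the rate (assumed) | Percentage shown |
|---|---|
| 30% | 3.0% |
| 50% | 5.0% |
| 64% | 6.4% |
| 84% | 8.4% |
| 90% | 9.0% |
| 100% (as at 0.3 mL/kg/h) | 10.0% |

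In counts, with about 70 treated (SAP 3.5) and 64% exposed, 0.64 × 70 ≈ 45. Five subjects with an AE at that rate give 5/70 = 7.1% in the table and 5/45 = 11.1% among the exposed.

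**Step 2: where 64% and 84% come from.** The 64% is the share who tolerated 6 or 8 mL/kg/h. All 16 must have received at least 6, so 64% is a floor for exposure to at least 6 in that study. Five of the 25 had AEs that limited the rate, at rates the protocol does not give. If all five had received 6 and fell outside the 16, the share would be (16 + 5)/25 = 84%. Neither is a forecast for BT595.

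**Step 3: time at each rate.** Inputs are the dose volume (2 to 8 mL/kg, Protocol 6.2) and steps of 0.3, 1.4, 2, 4, 6 and 8 mL/kg/h. Step length is an assumption.

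- 30-minute steps, 4 mL/kg: the steps to 4 mL/kg/h use 0.15 + 0.70 + 1.00 + 2.00 = 3.85 mL/kg. The remaining 0.15 mL/kg takes 0.15/6 h = 1.5 min at 6, with none at 8.
- 30-minute steps, 8 mL/kg: the steps to 6 mL/kg/h use 3.85 + 3.00 = 6.85 mL/kg. The remaining 1.15 mL/kg takes 1.15/8 h = 8.6 min at 8.
- 5-minute steps, 8 mL/kg: the steps to 6 mL/kg/h use (0.3 + 1.4 + 2 + 4 + 6)/12 = 1.14 mL/kg. The remaining 6.86 mL/kg takes 6.86/8 h ≈ 51.4 min at 8, against 5 min at each lower rate.

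Time at the top rate can therefore be much shorter or much longer than time at lower rates, depending on the steps used.

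**The case against.** - **Exposure by rate is not absent.** A reader might infer that none is planned, but SAP 11.1 tabulates the highest rate given. If that is per subject, adding the categories from the top down gives the number who reached each one. This stands. What is missing is the unit, the link to the AE table, and time at each rate.
- **A reader might conclude that high rates will look safer than they are.** Against exposed subjects that holds whenever some never reach the rate. Per unit time it does not follow: 30 minutes is stated only for the first two steps, the protocol lets intervals be shortened from the second infusion, and Step 3 shows the comparison can reverse.
- **64% is not an estimate of exposure here.** It describes tolerance of another product at the fourth infusion. The present study plans 18 infusions (Visits 2 to 19) or 14 (Visits 2 to 15), with more chances to reach high rates, so dilution could be smaller.
- **The denominator is inferred.** The sentence in 11.3 names none, and the table shells are in a separate document not available here. If they already use exposed subjects, the SAP text should say so.
- **Little formal weight rests on the table.** Safety results are descriptive, the counts are unaffected, and the criterion of an upper limit below 0.4 uses infusions as its base and does not change.

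These points narrow the concern. They do not remove the dilution that follows from the SAP's written rule.

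**Conclusion.** The point holds for the percentage of subjects. As the SAP is written, the by-rate percentage equals the share exposed times the risk among the exposed. It is understated by 36% in relative terms if 64% reach the rate, by 16% if 84% do, and not at all at 0.3 mL/kg/h. The size depends on the share of BT595 subjects who reach each rate, which is unknown in advance. The conclusion assumes the shells do not override the default.

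The documents do not support a claim about bias per unit time, because the steps actually used decide its direction. The primary analysis and the infusion-based safety criterion are unaffected. The change is worth making because the table addresses a question the study says it will assess, and the data needed are already collected.

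**What to change.** In SAP 11.3, override the default denominator for this table. For each rate category:

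1. Give the number of subjects and the number of infusions that actually received it, and use these as denominators.
2. Give total time at the rate, and AEs per infusion-hour, derived from the recorded rate-change times.
3. Keep the counts as planned.

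In SAP 11.1, state whether the highest rate given is tabulated per subject or per infusion. Align the shells with both sections.

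The cost is SAP wording and some extra programming to derive exposure by rate; no new data are needed. There are two downsides to state with the table. Denominators at the top rates may be small, so those percentages will be imprecise. The comparison across rates also stays descriptive, because only subjects who tolerated lower rates go on to higher ones.
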